Type 2 Diabetes Mellitus represents one of the most important health emergencies of this century. It is estimated that in 2019, there were already 463 million people with diabetes mellitus worldwide and this figure may increase to 578 million by 2030 and to 700 million by 2045. A state of hyperglycemia is associated with acute and chronic complications, in both cases affecting the cardiovascular system, mainly the blood vessels and consequently to the entire organism, but mainly to the eyes, kidneys, arteriovelocity systems and peripheral nerves. Although it is known that insulin resistance is reversible and that diabetes mellitus type 2 is controllable with a change towards a healthy lifestyle, the population ignores these recommendations and continue with their unhealthy habits. Thus, the number of patients continues to grow exponentially, which leads to an increase in economic expenditure in terms of health. This is why non-pharmacological measures are sought that favor the reduction of glycemia in patients with Diabetes Mellitus where the consumption of functional foods is a good alternative for the treatment of this chronic disease (Tinajero et al., 2021; Wu et al., 2014). Flaxseed is a food characterized by its nutritional properties, highlighting its content of alpha linoleic acid, flax lignans, and secoisolariciresinol diglucosides. The latter have antioxidant, lipid-lowering and hypoglycemic effects, which makes it an excellent option as a dietary supplement for treatment of type 2 diabetes (Parikh et al., 2019).

Some studies have been conducted with flaxseed supplementation. In a randomized cross-sectional study conducted by Tharwat et al., in 2017, evaluated 90 patients with type 2 Diabetes Mellitus with a range of 5 to 7 years of diagnosis

that they received oral hypoglycemic agents (metformin 500 mg) 3 times a day, having an age range between 35 and 45 years old. They divided the population into 3 groups:

Group 1 selected 30 patients with a calculated diet to 1350kcal (in the form of 50% carbohydrates, 30% fat and 20% protein) without flaxseed supplementation.

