Group 2 included 30 patients with the same diet, but adding linseed oil for 6 days a week in an amount of 13g/day. And in group 3, 30 patients were included in the same dietary regimen that group 1, adding flaxseed flour to their diet for 6 days a week, providing 32g of flaxseed per day. They concluded that in the 3 groups there was a reduction in blood glucose, however the decrease in glucose in Fasting reported by group 3 had better target figure achievements (Tharwat., 2017).

In a systemic review in 2018 Mohammadi et al, evaluated 25 randomized clinical trials, presenting a significant association between flaxseed supplementation and a reduction in blood glucose. It is worth mentioning that this relationship was more significant in the groups in trials that used ground flaxseed and reported an administration between 4 to 14 grams. (Mohammad., et al, 2018)

Hasaniani et al in 2019 conducted a randomized, controlled clinical trial with 57 patients with Diabetes Mellitus type 2. He divided his population into 2 groups. One group was prescribed 200g of natural yogurt in their diet and the other. Another group was also prescribed 200g natural yogurt with 30g of flaxseed added for 8 weeks documented a significant reduction in hemoglobin A1c ($p=0.001$) compared to the control group (Ha-saniani, 2019). In another study, Nowak concluded that regular consumption of flax seed improves the lipid profile by reducing triglycerides and total cholesterol and increasing HDL cholesterol (Nowak & Jeziorek., 2023)

5. Design of the research methodology.

Randomized clinical trial (case-control).

The sample will be recruited by self-selection.

The total number of recruited participants will be divided into two groups (A and B).

The control group will be given a talk nutritional education using the healthy eating plate and the intervention group will be instructed on supplementation with flaxseed (16 gr of flaxseed/day for three months) and also a nutritional education talk using the plate of good eating.

Once they sign the legal informed consent for participation, a clinical history will be applied where

Sociodemographic variables such as age, sex, occupation and marital status will be

asked. Clinical characteristics such as time since the disease has been on the disease, type of current diabetes treatment, control and comorbidities will also be asked. These variables will be collected at the beginning of the research and only once during the study.

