The nutritionist will take the participant's weight and height and record them at the beginning and end of the study.

Specialized nurses will take 5 milliliters of blood in the clinical laboratory area of the Regional Hospital

from the of Oaxaca and a clinical chemist professional will assess the biochemical parameters glucose, hemoglobin glycosylated, total cholesterol, triglycerides, LDL cholesterol and HDL cholesterol of each participant, at the beginning and at the end of the study (after three months of intervention, consuming 16 g of flaxseed/day).

The effect of flaxseed consumption on biochemical markers (glucose, hemoglobin) will subsequently be evaluated.

glycosylated, total cholesterol, triglycerides, LDL cholesterol and HDL cholesterol and the possible combinations will be analyzed (pharmacological + non-pharmacological) most effective for the treatment of type 2 diabetes.

6. Selection criteria and description of participants.

Selection criteria

Patients living with type 2 Diabetes Mellitus and who come with fasting blood glucose greater than 140 and hemoglobin glycosylated greater than 6.5%, who are beneficiaries who attend the Nutrition outpatient clinic of the Hospital-Regional "Presidente Benito Juárez" diagnosed at most one year ago and who agree to participate in the study, age between 45 and 65 years with regular attendance at the outpatient clinic, minimum of 3 consecutive months.

7. Methods of selection and inclusion of participants in the study.

Phase 1. Sample recruitment.

The convenience sample will be recruited by self-selection: patients who attend the nutrition outpatient clinic that meet the inclusion criteria, they will be invited to participate in the study. After giving them all information, those who wish to participate will sign the legal informed consent for participation.

Phase 2. Case randomization procedure.

Patients who sign the informed consent will be assigned a group according to the following: in the case

If you have an even number in your file, you will be part of the control group (A), and if you have an odd number, you will be part of intervention group B.

Group A.

They will be given verbal instructions to continue with the treatment established by the treating physician, and they will be provided with nutritional guidance with the help of the healthy eating plate.

Group B.

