They will be given verbal instructions to continue with the treatment established by the treating physician, they will be given nutritional guidance with the help of the healthy eating plate and they will be provided with a pamphlet with the instructions. written and photographed on how to consume flaxseed and its benefits.

Phase 3.

Administration of flaxseed

Researchers will purchase, package, and provide flaxseed powder to members of group B. Flaxseed will be delivered in packages with 16 gr of ground flaxseed each, which will be given to patients for their daily consumption (a tablespoon of 8

gr of flaxseed in the morning snack and 8 gr of flaxseed in the afternoon snack)

(late). You will be provided with brochures with images explaining how to consume it and how the glass should look when finished. Various forms of consumption of the powder will also be provided to avoid getting bored with the taste and consistency. from dust.

Phase 4.

Surveillance and monitoring.

Daily contact will be maintained with participants via WhatsApp in order to remind them to take flaxseed.

and also to find out if they have any adverse symptoms (abdominal distension, flatulence, gas, diarrhea, etc.), as well as to resolve doubts and ask if they should start taking some vitamins, minerals or medications.

Both groups will be given a 24-hour recall and a food frequency questionnaire. every 15 days. The food consumption of both groups will be analyzed according to its nutritional content (energy, macro and micronutrients) and each nutrient will be used as a nutritional variable that can influence the control of the biochemical markers.

Phase 5.

Data analysis.

Statistical analysis will be performed using the IBM SPSS Statistics program version 24, in which it will be performed descriptive statistics and for group comparisons different tests will be performed depending on the nature of the variables. The comparison between the values measured at the beginning and the values measured after 3 months in each group will be performed using the paired t test and will be

considered statistically significant when $p < 0.05$.

Inclusion criteria:

- ÿ Patients entitled to who attend the “Presidente” Regional Nutrition outpatient clinic Benito Juárez” diagnosed at most one year ago and who agree to participate in the study by signing the informed consent.
- ÿ Patients diagnosed with uncontrolled Diabetes Mellitus evidenced by biochemical markers, den-

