within a maximum of 1 month of validity, (fasting blood glucose greater than 140 and glycosylated hemoglobin greater than (6.5%).
- ÿ Patients with regular attendance at the outpatient clinic for at least 3 consecutive months.

Exclusion criteria:

- ÿ Patients diagnosed with chronic kidney disease undergoing renal function replacement therapy.
- ÿ Patients who already consume enough fiber and omega 3, as evidenced by the application of a reminder of 24 hours and a food frequency questionnaire.
- ÿ Pregnant or
breastfeeding women.
- ÿ Patients in
menopause.
- ÿ Patients with glucose disorders secondary to autoimmune diabetes, thyroid diseases or insulin-producing tumors.
- ÿ Patients with a medical history of poor drug adherence.
- ÿ Patients with adequate glycemic control evidenced by clinical laboratory tests for at least 2 months.
- ÿ Patients who cannot read or write.

ÿ Patients who do not have a means of contact for follow-up.

Elimination criteria:

ÿ Patients who do not agree to participate in the study. ÿ Data collection instrument with incomplete items.

ÿ People who voluntarily withdraw from the study at any time. ÿ If the patient has surgery during the study.

ÿ Patient who during the study begins to consume any type of supplement (vitamins, minerals, omega 3).

ÿ Patient who stops consuming flaxseed during the study.

8. Experience of the principal investigator and co-investigators in this type of research.

(maximum)

The principal investigator has participated in different research projects in the area, both as a collaborator and as principal investigator:

-Collaborating researcher. Faculty of Nutrition. Universidad Veracruzana. **“Evaluation of waist circumference in fifth period students of proposal 3 and 4 as a risk factor for developing metabolic syndrome”**. Faculty of Nutrition. Xalapa, Universidad Veracruzana, Mexico. 2010. SATISFACTORILY COMPLETED

-Collaborating researcher. Cooperation with the Coordination of the Master's Degree in Food and Nutritional Security.

“Influence of maternal nutrition on the programming of fetal adipose tissue development”. Faculty of Nutrition. Universidad Veracruzana. 2011. SATISFACTORILY COMPLETED

-Collaborating Researcher. **“Influence of physical activity on biochemical and vascular factors determining endothelial dysfunction in postmenopausal women”**. Sant Joan de Reus University Hospital, Tarragona, Spain, 2012. SATISFACTORY COMPLETED

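### Starting a supplement after allocation eliminates the patient, so the groups compared need not be the groups allocated; and diabetes drug treatment is recorded only at baseline

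*Protocol*

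**What the plan says.** **The rule.** Among the elimination criteria in section 7 of the protocol is a "Patient who during the study begins to consume any type of supplement (vitamins, minerals, omega 3"). It is not limited to one group. The same list contains "If the patient has surgery during the study" and "Patient who stops consuming flaxseed during the study", together with withdrawal, non-agreement and an incompletely filled data-collection form. No item concerns starting or changing a drug.

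**Allocation.** In section 7, Phase 2, patients who have consented are assigned by the parity of their file number. Both groups receive dietary guidance, and of their usual care the protocol says: "They will be given verbal instructions to continue with the treatment established by the treating physician". Only group B receives flaxseed powder and a pamphlet. No placebo or masking of patients is described.

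**Monitoring.** Phase 4 states: "Daily contact will be maintained with participants via WhatsApp in order to remind them to take flaxseed". The same contact is to find out about symptoms and to "ask if they should start taking some vitamins, minerals or medications". Both groups also complete a diet recall and a food-frequency questionnaire every 15 days.

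**Recording of drug treatment.** Section 5 lists current diabetes treatment among the clinical history items and then says: "These variables will be collected at the beginning of the research and only once during the study". Specific objective 7 and section 5 nevertheless plan an analysis of which drug plus non-drug combinations work best.

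**The concern.** Starting a supplement is something the patient does after allocation, knowing the group. Patients enter because their diabetes is uncontrolled. A control who received only advice may look for a product. A flaxseed patient with the bowel symptoms foreseen in section 9 may look for a different one. The decision can therefore depend both on group and on how the patient is doing. If such patients are dropped, the retained groups are selected on that decision, and their difference mixes the flaxseed effect with the selection.

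The second matter is one of recording. Drug treatment can change within three months in an uncontrolled population, and the outcomes are the markers that glucose- and lipid-lowering drugs target. With treatment type collected only at baseline, the planned analysis of combinations would classify patients by the treatment they entered on, which may not be the one they were taking at month 3.

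**Working it through.** **1. Is the event after allocation?** Yes. Assignment follows consent (section 7, Phase 2), and the rule concerns supplements begun during the study.

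**2. Does elimination mean leaving the analysis?** The protocol does not say so in words. It is the natural reading, because the same list includes withdrawal and incomplete data forms. Section 5 plans the end-of-study blood sample for every participant, but nothing says that it is still taken once a patient has been eliminated.

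**3. What does removal do to the contrast?** The protocol states no sample size, effect size, SD or elimination rate, so there is no figure to reproduce. Algebraically, let e_A and e_B be the shares removed, and d_A and d_B the mean outcome of removed minus kept patients.

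- Full-group mean = kept mean + e × d, so the kept mean differs from the full-group mean by −e × d.
- Shift in the contrast (B minus A) = e_A × d_A − e_B × d_B.
- With a common gap d, shift = (e_A − e_B) × d.

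All inputs below are assumptions, in SD units of the outcome:

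| Difference in share removed | d = 0.25 | d = 0.5 | d = 1.0 |
|---|---|---|---|
| 0.05 | 0.0125 | 0.025 | 0.05 |
| 0.10 | 0.025 | 0.05 | 0.10 |
| 0.20 | 0.05 | 0.10 | 0.20 |

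- Equal shares and an equal gap: shift = 0.
- Equal shares of 0.10 with gaps of 0.5 and 0.25: 0.10 × (0.5 − 0.25) = 0.025 SD. Equal numbers removed are therefore not sufficient for balance.

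On the HbA1c scale, again with assumed inputs, a share of 5% and a gap of 0.3 points gives 0.05 × 0.3 = 0.015 points, and 25% with 0.8 points gives 0.25 × 0.8 = 0.20 points. These are shifts in one group's mean. They become shifts in the contrast only if the other group loses nobody, or loses patients with no outcome gap.

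**4. Are drug changes captured?** Three places bear on this. Section 5 collects treatment type once, at the start. Phase 2 tells patients to continue their treatment, which does not say how a change is recorded. Phase 4 mentions medications in the daily contact, but the translated sentence is ambiguous and names no record, date or use in the analysis. Set against specific objective 7, no systematic record of drug changes is specified.

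**The case against.** The strongest reply is that the rule is worded identically for both groups, with no documented difference in how often it would apply. The suggested mechanisms act in both arms, and equal removal with an equal gap leaves the contrast unbiased. This stands as a limit on size and direction. It does not rescue the rule, because equality of both quantities cannot be assumed when patients know their group and only one group receives a product.

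It may also be said that a SAP could define the analysis set. It could, but it cannot recover a month-3 sample that was never taken.

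A third reply is that the remedy overlaps with that for the flaxseed-stopping rule, which can act only in group B. That is true. The two rules are nevertheless separate, and amending one leaves the other in force.

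Four stronger readings are tempting and are not supported:

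- *A control who begins eating flaxseed would be eliminated.* Section 4 does describe flaxseed by saying "which makes it an excellent option as a dietary supplement for treatment of type 2 diabetes", but the rule carries its own gloss of vitamins, minerals and omega 3, and the same section calls flaxseed a food. If flaxseed counted as a supplement, all of group B would be eliminated on starting it.
- *Patients whose drugs change ought to be removed as well.* Removal on post-allocation events is the problem, so keeping these patients is consistent with an as-allocated comparison. Only the recording is deficient.
- *Group B is watched more closely, so more of its supplement starts are found.* The stated purpose of the daily contact fits only group B, yet the text says participants without restriction. Unequal detection is possible but not established.
- *The bias is up to 0.20 HbA1c points.* That figure rests entirely on assumed inputs and describes one group's mean.

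**Conclusion.** The concern holds in two limited parts. First, eliminating supplement starters filters the groups on a post-allocation choice, so the patients compared need not be those allocated. The contrast is biased if the share removed or the outcome gap differs between groups. This assumes that elimination means leaving follow-up and analysis, as the list suggests. Neither size nor direction can be derived from the protocol; the range of about 0.01 to 0.20 SD is illustrative only, and zero is possible. Second, drug treatment is recorded once, at baseline, which is insufficient for the planned analysis of drug plus non-drug combinations. The protocol should be amended on both because the change is cheap and a missed month-3 sample cannot be replaced.

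**What to change.** 1. Remove supplement start as a reason for elimination from follow-up and from the main analysis.
2. Take the month-3 blood sample already planned for each participant, and analyse every patient in the group allocated.
3. At the existing 15-day contacts, record supplement starts and changes in glucose- or lipid-lowering drugs, with product and date, in the same way in both groups. Use this record, alongside the baseline entry, in the analysis of combinations.
4. Report a sensitivity analysis that excludes or flags patients with such a start or change, under one rule for both groups.

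This concerns retention, recording and analysis only; it sets no rule on what patients may take. The cost is one amended criterion and a short addition to a questionnaire already in use. The planned sample needs no new procedure. The downside is that supplement users stay in the main comparison and may slightly dilute the contrast; the sensitivity analysis shows how far the result depends on them.

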To minimize risks, researchers will be in daily contact with participants to warn them any damage to health and to know if any gastrointestinal reaction or even allergic reaction occurs, this in order to be able to tell you what to do or even stop the study if necessary. In case the discomfort persists, the responsibility of the research team will be guaranteed to provide immediate nutritional care to the participant (as established in articles 18 and 19 of the Regulations) of the General Health Law on Health Research).

The risk management process will be as follows:

1. Identify risk	The patient will be monitored in case of any health problems caused by flaxseed.
2. Analyze	The symptom will be analyzed.
3. Prioritize risk	It will be verified that your health is not compromised.
4. Control the risk	If the symptom is controllable, the treatment will continue and if it is not, the patient can withdraw.

of the study. If the patient presents any

stress problems due to the administration
tion is withdrawn from the study.

11. Procedure by which consent to participate in the study will be obtained.

- Participants who meet the inclusion criteria will be recruited in the nutrition outpatient clinic from the Regional Hospital of Oaxaca.
- You will be provided with detailed information about the study and will be provided with written informed consent/legal participation document (ANNEX 1)
- You will be given time to proceed with the reading of the document and you will have time in case the participant has doubts or questions about the study.

12. Management of confidentiality of information.

Upon entering the study, each participant will be registered with a number by which they will be addressed throughout the study. All data will be treated anonymously.

13. Conflicts of interest.

There is no conflict of interest

14. Bibliography

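### Eliminating patients who stop flaxseed acts after allocation and can reach only group B, so the groups analysed are not the groups allocated

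*Protocol*

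**What the plan says.** Section 7, Phase 2, fixes the time of allocation: "Patients who sign the informed consent will be assigned a group according to the following", namely by even or odd file number. Phase 3 gives the product to one arm only: "Researchers will purchase, package, and provide flaxseed powder to members of group B". Group A receives usual treatment and eating-plate guidance.

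The elimination criteria at the end of section 7 then remove patients for later events. One is "Patient who stops consuming flaxseed during the study"; another is "People who voluntarily withdraw from the study at any time". The remaining four are not agreeing to take part, an incomplete data collection instrument, surgery, and starting a supplement.

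Section 9 expects constipation, diarrhoea or gastrointestinal upset from flaxseed. Section 10 links symptoms to leaving: "If the symptom is controllable, the treatment will continue and if it is not, the patient can withdraw". Phase 3 also takes a step against loss of interest in the product: "Various forms of consumption of the powder will also be provided to avoid getting bored with the taste and consistency".

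For the analysis, Phase 5 says that the comparison of baseline and 3-month values "in each group will be performed using the paired t test", and leaves group comparisons to tests chosen by type of variable. Section 5 plans the blood measurements "of each participant, at the beginning and at the end of the study", but does not say whether this covers a patient who has been eliminated.

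**The concern.** A rule that removes patients for what they do after allocation is harmless only if those removed resemble those kept, or if the same kind of patient is removed from both arms. Neither can be assumed here. Patients who stop because of symptoms or lack of persistence may well differ in diet, drug adherence and glycaemic course from those who continue. Their counterparts in group A cannot be identified and stay in the comparison.

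The between-group difference would then mix any effect of flaxseed with the difference between persistent patients and all patients. Group B's before-after change would likewise describe only those who kept going. The protocol's summary says that a positive result could lead to flaxseed being offered in place of, or together with, drug treatment. A result that leaves out patients who could not keep taking it does not describe the effect of offering it.

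**Working it through.** **Step 1: which arm each criterion can reach**

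| Elimination criterion | Group A | Group B |
|---|---|---|
| Does not agree to take part | yes | yes |
| Incomplete instrument | yes | yes |
| Voluntary withdrawal | yes | yes |
| Surgery | yes | yes |
| Starts a supplement | yes | yes |
| Stops flaxseed | no (none supplied) | yes |

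One of the six can reach only group B, and none can reach only group A. No criterion removes a group A patient for ignoring the dietary guidance.

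**Step 2: size of the bias**

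The protocol states no sample size, SD, effect size or stopping rate, so there is no figure to reproduce and all inputs below are assumptions. Let a fraction q of group B stop. Let the mean improvement be m in those who continue and m − d in those who stop, in SD units of the outcome analysed (3-month value or change).

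- Group B as allocated: (1 − q)m + q(m − d) = m − qd
- Group B after elimination: m
- Bias toward flaxseed: m − (m − qd) = **q × d**

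With no true effect, group A has the same mix of patients and mean m − qd, so the comparison is off by q × d. On the change scale, the mean entering group B's paired test shifts by the same amount.

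**Step 3: false-positive rate with no true effect**

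Simulation of 100,000 trials per case: total variance 1, same mix of potential stoppers in both arms, two-sided 5% two-sample t test, all of group A against group B without stoppers. The protocol gives p < 0.05 without stating sidedness. The rates are the chance of a significant result favouring flaxseed (nominal 2.5%).

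| q | d (SD) | Bias (SD) | 30 per arm | 60 per arm |
|---|---|---|---|---|
| 10% | 0.25 | 0.025 | 3.1% | 3.4% |
| 20% | 0.25 | 0.05 | 3.7% | 4.4% |
| 20% | 0.5 | 0.10 | 5.4% | 7.3% |
| 30% | 0.5 | 0.15 | 7.5% | 11.4% |
| 20% | 0 | 0 | 2.5% | 2.4% |
| 20% | −0.25 | −0.05 | 1.6% | 1.3% |

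With all allocated patients analysed, the rate is 2.5% to 2.6% in every case.

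Hand check for q = 20%, d = 0.5, 30 per arm: the variance among continuers is 1 − 0.2 × 0.8 × 0.5² = 0.96, and 24 patients remain in group B. The standard error is √(1/30 + 0.96/24) = 0.271, the shift is 0.10/0.271 = 0.37, and P(Z > 1.96 − 0.37) is about 5.6%, close to the simulated 5.4%.

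**Step 4: a second model**

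Suppose instead that the fraction q with the lowest propensity to adhere is removed, and that propensity correlates ρ with improvement. The bias is ρ × φ(z_q)/(1 − q), where φ is the standard normal density and z_q its q quantile. For q = 20% and ρ = 0.4 this is 0.4 × 0.280/0.8 = 0.14 SD. Over q of 10% to 30% and ρ of 0.2 to 0.4, the bias runs from 0.04 to 0.20 SD. The two-sided false-positive rate (nominal 5%) runs from 5.2% to 11.0% with 30 per group and from 5.8% to 25.7% with 100. With ρ = 0 there is no bias. In both models the bias does not shrink as the trial grows, so its effect on the error rate increases with sample size.

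**The case against.** The strongest reply has five parts.

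- **The size is assumed.** Stopping rate, prognosis difference and arm sizes are not in the protocol. Daily reminders and the exclusion of patients with a history of poor drug adherence may keep stopping low. This stands, so the figures are illustrations. Boredom is also mentioned only as something to prevent.
- **Intolerance leaves by another door.** Under section 10, a patient with uncontrollable symptoms can withdraw, and one with stress problems due to the administration is withdrawn. Deleting the flaxseed criterion alone would leave these exits, which also arise from flaxseed. This stands, and it is why the fix covers follow-up after every post-allocation event rather than one line of the list.
- **The aim is the effect of consuming flaxseed.** Objective 4 refers to markers after regular consumption. That is a legitimate question, but dropping stoppers from one arm does not answer it without bias, because group A still contains the matching patients.
- **A SAP may define the analysis sets.** It may, and a missing set is not the complaint. The protocol states a removal rule that a SAP keeping these patients would contradict. The protocol does not define elimination, but the natural reading is removal from the study and its data, as the neighbouring item on incomplete instruments suggests. If follow-up also ends, a SAP would have no 3-month value to use.
- **Allocation by file number is itself open to question.** The simulation does assume that the arms are alike at allocation. That is a separate matter and does not justify a further selection.

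**Conclusion.** The concern holds. That the rule acts after allocation and on one arm follows from the protocol's text and needs no assumption. The likely direction favours flaxseed, if patients who persist would have improved more anyway, but the protocol fixes neither direction nor size. Under the assumed q × d model, the bias runs from −0.05 to 0.15 SD. The chance of falsely favouring flaxseed is 1.6% to 7.5% with 30 per arm and 1.3% to 11.4% with 60, against 2.5%. These rates are for a two-sample t test; none was computed for the paired test. The point must be fixed in the protocol, because a 3-month sample that was never taken cannot be recovered at analysis.

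**What to change.** Replace the post-allocation elimination criteria with a follow-up and analysis rule:

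- Every allocated patient is analysed in the assigned group.
- The planned 3-month blood sample is taken and used whether or not flaxseed was stopped, a supplement was started, surgery took place or a questionnaire is incomplete, unless consent is withdrawn.
- These events, and the reasons for stopping, are recorded and reported by arm.
- The present criteria define only a supportive per-protocol analysis.
- Where consent is withdrawn, the number is reported by arm, and missing values in group B are not filled in as if those patients had been adherent completers.

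Section 10 should be worded to agree, so that ending flaxseed and ending follow-up are distinct. None of this changes who may stop flaxseed or leave the study. The protection extends only as far as the 3-month samples are actually obtained.

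The cost is a short amendment and some effort to bring back patients who stop. The statistical price is dilution. If 10%, 20% or 30% of group B stop and gain nothing (assumed), the estimate is 1 − q = 90%, 80% or 70% of the full-adherence effect. Equal power then needs 1/(1 − q)² = 1.23, 1.56 or 2.04 times the sample that full adherence would need. Against the present plan, which already loses those patients from group B, the factor is [2/(1 − q)²]/[1 + 1/(1 − q)] = 1.17, 1.39 or 1.68 (for q = 20%: 3.125/2.25 = 1.39).
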